8.1.6.2 Secondary Efficacy Variables

All secondary efficacy variables are listed in Section 5.3.3.2.

In general, continuous secondary efficacy variables with repeated measurements will be analyzed using a Mixed Effect Repeated Measure (MMRM) model. Continuous secondary efficacy variables which are collected at only one post-baseline visit (such as Mayo score) will be analyzed using an Analysis of Covariance (ANCOVA) model. Categorical secondary efficacy variables will be analyzed using the CMH test controlling for stratification variables. NRI-C for missing data will be used for categorical secondary endpoints.

The primary analysis and ranked secondary analysis in each substudy will be repeated in the ITT analysis sets as defined in Section 8.1.1, as appropriate.

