13.0 Version History

Table 1. SAP Version History Summary

Version	Date	Summary
1.0	17 July 2018	Original version
2.0	13 July 2020	
 • Revised the SAP per the latest SAP template. • The following changes have occurred in order to reflect changes in the protocol amendment and regulatory guideline. 
 ○ Updated secondary endpoints: added histologic-endoscopic mucosal improvement, change from baseline in IBDQ total score and change from baseline in FACIT-F score; moved response in IBDQ Bowel Symptom domain, UC-related hospitalizations and surgeries and response in IBDQ fatigue item to other efficacy endpoints. ○ Non-ranked secondary endpoints are now listed under Other Efficacy Endpoints. ○ Added NRI-C method for handling missing data due to COVID-19. NRI-C will be used for the primary efficacy analysis and NRI-NC will be considered as sensitivity analysis. ○ Removed the Last Observation Carried Forward (LOCF) approach from the missing data imputation as LOCF potentially can result in a biased estimation of treatment effect and underestimate the variability. ○ Removed Holm procedure from the multiplicity control method as the number of ranked secondary endpoints was reduced. ○ Added the bio-IR and non-bio-IR subgroup analysis for the secondary endpoints: endoscopic remission, endoscopic improvement and clinical response per adapted Mayo score. ○ Remove subgroup analyses including Baseline immunosuppressant use (yes, no), Baseline Adapted Mayo Score (\leq median, $>$ median), Baseline Full Mayo Score (\leq median, $>$ median), Baseline hs-CRP (\leq median, $>$ median), Baseline fecal calprotectin (\leq 150 mg/kg, $>$ 150 mg/kg), Baseline fecal calprotectin (\leq median, $>$ median), and Baseline albumin (\leq median, $>$ median).
3.0	16 September 2020	
 • Added definitions of estimand for primary and key secondary endpoints. • Clarified the MI method to handle missing data due to COVID-19 and other reasons.

Table 1. SAP Version History Summary (Continued)

Version	Date	Summary
4.0	05 November 2020	
 Added supplementary analysis for the primary endpoint to exclude subjects with deviations that could potentially impact the primary analysis.
5.0	13 November 2020	
 Added exclusion of subjects from efficacy analysis due to site non-compliance.

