2. Missing values after Study Day 1 will be imputed using the latest non-missing values after Day 1 and prior to the missing value. If there are no non-missing values after Baseline, then the LOCF value will be missing.

Hybrid Multiple Imputation Method

Primary endpoint of clinical remission will be analyzed using hybrid multiple imputation method. Subjects who discontinue prior to Week 8 due to lack of efficacy or AEs will be

considered as "not achieved" for clinical remission. Subjects who discontinue for other reasons will be categorized according to multiple imputations.

Mixed-Effect Model Repeated Measure (MMRM)

The MMRM model will be used for continuous efficacy variables with longitudinal data as the primary analysis. The MMRM model includes the baseline values as covariate; randomization stratification factors, treatment, time point and treatment-by-time point interaction as fixed effects; and subjects within treatment as random effect. An unstructured (co)variance structure will be used to model the within subject error. The comparison at a time point will be the contrast between treatments at that time point. Satterthwaite's approximation will be used to estimate denominator degrees of freedom.

Observed Case (OC)

Observed case analysis will be performed such that missing values will not be imputed.

Imputation of Missing Dates

For Baseline, efficacy, and safety parameters, if the day and/or month are missing, the following conventions will be used to impute the missing dates:

- 01 for missing start day
- End of month for missing end day
- January 1st for missing start month
- December 31st for missing end month

In case of partially missing AE start and stop dates, the dates will be imputed by comparing to first dose date of study medication so that the corresponding AEs will be made treatment-emergent whenever possible. If the start date of an AE is partially missing and the month is the same as the start date of a new therapy, the AE will be made treatment emergent to the new therapy.

In case of missing or partially missing study drug dosing dates, the dates will not be imputed. Subjects will be treated as not receiving dose on that date.

Rules for Calculation of Stool Frequency Subscore and Rectal Bleeding Subscore

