- Proportion of subjects with fecal calprotectin below 150 mg/kg over time.
- Proportion of subjects with IBDQ response (increase of IBDQ ≥ 16 from Baseline) over time.
- Change from Baseline in hs-CRP over time.
- Change from Baseline in fecal calprotectin over time
- Change from Baseline in Adapted Mayo score, Full Mayo score, Partial Mayo score and Mayo subscores over time.
- Change from Baseline in UCEIS score over time.
- Proportion of subjects with histologic remission (defined as Geboes score < 2) at Weeks 8 and 44.
- Change from Baseline in histologic score over time.
- Change from Baseline in laboratory and nutritional parameters (e.g., hemoglobin, hematocrit, albumin, total protein concentration, and weight).
- Change from Baseline in subject-reported stool frequency (absolute values).
- Change from Baseline in IBDQ score over time.
- Change from Baseline in EQ-5D-5L score over time.
- Change from Baseline in WPAI scores over time.
- Change from Baseline in SF-36 PCS, MCS components and domain scores over time.
- Change in PGIC score over time.

- Change from Baseline in FACIT-F score over time.
- Change from Baseline in UC-SQ score over time
- Health care resource utilization (UC-related hospitalizations and surgeries) during the study.

For categorical efficacy endpoints, the pairwise comparisons for the difference in proportions of subjects between treatment groups and placebo group will be analyzed using the CMH test adjusted for previous biologic use, baseline corticosteroid use and baseline Adapted Mayo score (≤ 7 and > 7). Additionally, the CMH based two-sided 95% confidence interval (CI) for the difference in the proportions between the treatment groups and placebo group will be provided.

The non-responder imputation will be used for subjects with missing data at the endpoint evaluated. The last observation carried forward (LOCF) method will also be used as the sensitivity analyses for the secondary endpoints.

Continuous secondary efficacy variables will be analyzed using an Analysis of Covariance (ANCOVA) model including factors for treatment group and stratification variables. Baseline values will be used as a covariate in the ANCOVA models.

Both last observation carried forward (LOCF) and observed case (OC) analyses will be used for continuous endpoints when conducting ANCOVA analysis. The LOCF analysis is considered primary for inferential purposes. HCRU will be analyzed as observed only.

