Continuous secondary efficacy variables with repeated measurements will also be analyzed using a Mixed Effect Model Repeated Measurement (MMRM). The baseline values to be included in MMRM are sex, age, disease duration, Baseline IMM use, Baseline hs-CRP. The comparison at a time point will be the contrast between treatments at that time point.

For HCRU, the number and percentage of hospitalizations and surgeries (all-cause and UC-related) will be calculated for each treatment group and placebo group. Differences

in the risk of hospitalization and surgeries will be compared between treatment groups and placebo group using Chi-square test.

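### For repeated continuous endpoints the Substudy 1 SAP makes MMRM primary in one section and ANCOVA with LOCF primary in another, and describes the MMRM covariates in two ways it does not reconcile

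*SAP*

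**What the plan says.** Section 6.0 of the Substudy 1 SAP, under its missing-data conventions, states: "The MMRM model will be used for continuous efficacy variables with longitudinal data as the primary analysis". It then specifies that model: "The MMRM model includes the baseline values as covariate; randomization stratification factors, treatment, time point and treatment-by-time point interaction as fixed effects".

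Section 10.3 of the same SAP takes a different route. It states: "Continuous secondary efficacy variables will be analyzed using an Analysis of Covariance (ANCOVA) model including factors for treatment group and stratification variables", and the sentence after it adds the baseline value as a covariate. It does not limit ANCOVA to endpoints with a single post-baseline visit. On missing data it says: "Both last observation carried forward (LOCF) and observed case (OC) analyses will be used for continuous endpoints when conducting ANCOVA analysis", and then: "The LOCF analysis is considered primary for inferential purposes". Only after that does it say that variables with repeated measurements will, in addition, be analysed by MMRM. For that model it gives a different covariate statement: "The baseline values to be included in MMRM are sex, age, disease duration, Baseline IMM use, Baseline hs-CRP".

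Section 10.4 tests all pairwise comparisons with placebo at a nominal two-sided 0.05, with no multiplicity adjustment.

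Two other places show the sponsor's general position. Protocol Section 8.1.6.2 says that, as a rule, "continuous secondary efficacy variables with repeated measurements will be analyzed using a Mixed Effect Repeated Measure (MMRM) model", and keeps ANCOVA for variables collected at one post-baseline visit. The version histories of the Substudy 2 and Substudy 3 SAPs explain why LOCF was removed there: "LOCF potentially can result in a biased estimation of treatment effect and underestimate the variability".

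**The concern.** A SAP should let two programmers working independently arrive at the same primary estimate for each endpoint. Here one programmer could follow Section 6.0 and report MMRM, while another could follow Section 10.3 and report ANCOVA on LOCF data. Each could point to a sentence that calls their result primary.

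The two methods treat dropout differently. MMRM uses the observed visits under a missing-at-random assumption. LOCF freezes a subject at the last post-baseline value and treats it as if observed at Week 8. With unequal dropout across four doses and placebo, the estimates and P values can differ, and the choice could be made after both are seen. The covariate question adds a second degree of freedom within MMRM itself.

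**Working it through.** No figure in the plan is in dispute, so the check sets the text side by side.

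**Step 1. Which method is primary?**

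| | SAP (Substudy 1) 6.0 | SAP (Substudy 1) 10.3 |
|---|---|---|
| Scope | Continuous variables with longitudinal data | All continuous secondary variables |
| Primary method | MMRM | ANCOVA, with LOCF primary for inference |
| Role of the other method | LOCF listed as an imputation method | MMRM run in addition, for repeated measurements |

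The scopes overlap on every continuous secondary variable with repeated post-baseline visits. No sentence gives one section precedence.

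**Step 2. Which endpoints fall in the overlap?** The visit-window tables in Section 6.0 settle this.

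- Partial Mayo score: Weeks 2, 4, 6 and 8, so repeated.
- hs-CRP and patient questionnaires such as IBDQ and SF-36: Weeks 2, 4 and 8, so repeated.
- Fecal calprotectin: Weeks 2 and 8, so repeated.
- Mayo score: Week 8 only (Rx Days 2 to 71), so not repeated.

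The only continuous variable among the seven ranked secondary endpoints is change in Full Mayo score (item 5). It has one post-baseline window, so the MMRM sentence does not reach it. The LOCF rules in Section 6.0 bar carrying baseline forward, so for a missed Week 8 visit LOCF and observed-case results coincide. The primary endpoint is binary and uses NRI, MCP-Mod and CMH (Section 10.2). The overlap therefore holds only non-ranked endpoints.

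**Step 3. Which MMRM?** Section 5.2 gives three stratification factors: previous biologic use, baseline corticosteroid use, and baseline Adapted Mayo score (≤ 7 or > 7).

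| Term | MMRM in 6.0 | List in 10.3 |
|---|---|---|
| Endpoint's own baseline | Yes | Not listed, except when hs-CRP is the endpoint |
| Stratification factors | All 3 | 0 of 3 listed |
| Sex, age, disease duration, immunosuppressant use, hs-CRP | Not listed | Listed |

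Three readings are open:

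- The five covariates are added to the Section 6.0 model.
- They spell out what Section 6.0 means by baseline values. The stratification factors then stay, but the endpoint's own baseline is unlisted except for hs-CRP.
- They replace both.

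The text does not choose among them. Adding the LOCF ANCOVA, 1 + 3 = 4 specifications can be defended from the SAP for each dose comparison on an affected endpoint, though they are not equally plausible.

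**The case against.** The best defence is that the LOCF sentence comes directly after one naming LOCF and observed-case as the two ways of running ANCOVA. Read in place, it ranks LOCF over observed-case within ANCOVA and says nothing about MMRM. That reading is fair, but it does not remove the conflict. Section 10.3 still assigns every continuous secondary variable to ANCOVA and runs MMRM only in addition, while Section 6.0 calls MMRM primary for the longitudinal ones.

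On covariates, a reader might infer that Section 10.3 removes the stratification factors and the endpoint's own baseline from the MMRM. The documents do not support that. The sentence does not say its list replaces anything, it does not mention the stratification factors, and hs-CRP is on the list as its own baseline. What stands is that the two descriptions are unreconciled.

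The comparison with other documents also has limits. This SAP was written to Protocol Amendment 2 of October 2017. The protocol in hand is later, and the sponsor's reason for dropping LOCF first appears in SAP versions from 2020 for other substudies. These support the direction of the fix; the contradiction itself lies wholly inside the Substudy 1 SAP. The current Protocol Section 8.1.3 still carries last values forward in Substudy 1 after corticosteroid initiation or escalation. That is a rule for an intercurrent event and does not make LOCF ANCOVA the primary analysis.

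Finally, the reach is narrow: a Phase 2b substudy, non-ranked endpoints and nominal testing. A reader might infer that the dose selection or the primary result is in doubt. Nothing here touches either.

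**Conclusion.** The Substudy 1 SAP is wrong as written for repeated continuous endpoints. It states two incompatible rules for which analysis is primary and leaves the MMRM covariates open. The conflict is confined to non-ranked endpoints, so it bears on how secondary results are reported and on no confirmatory claim. It is worth correcting but not critical.

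The numerical effect cannot be derived from the documents. The gap between LOCF ANCOVA and MMRM depends on how much data is missing and how unevenly across groups. Any loss of precision from the covariates depends on which reading was programmed and on how strongly each baseline predicts its outcome. The documents give neither.

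The conclusion assumes that the visit windows in Section 6.0 decide which variables count as repeated, and that no other document ranks the two sections.

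**What to change.** State once, in one place:

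- MMRM, with the endpoint's own baseline value and the three randomization stratification factors, is primary for continuous endpoints with repeated post-baseline visits.
- ANCOVA, with the baseline value and the same factors, is primary for continuous endpoints with one post-baseline visit.
- LOCF is a sensitivity analysis.
- The five covariates in Section 10.3 are additional to the model above, or the sentence is deleted.

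This follows the split in Protocol Section 8.1.6.2 and the sponsor's later position on LOCF.

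Substudy 1 induction is complete and the dose-selection analysis has been run, so a silent rewording would be a change made after unblinding. The correction should be a dated SAP addendum or a statement in the study report. It should name the method and covariates actually used as primary and show the other method beside them as sensitivity. If LOCF ANCOVA was reported as primary, the report should say so and present MMRM alongside.

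The cost is a short addendum or report paragraph, plus tables for whichever method was not produced. The documents do not say which models have been programmed. No new data are needed.

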10.4 Handling of Multiplicity

Substudy 1 is the Phase 2b randomized, placebo-controlled dose ranging study. The MCP step in MCPMod approach will typically be performed using an efficient test for trend, adjusting for the fact that multiple candidate dose response models are being considered. Pairwise comparisons between treatment groups and placebo group for the primary, the ranked secondary and non-ranked secondary efficacy variables will be analyzed at the nominal α level of 0.05 (two-sided). No multiplicity adjustment will be performed for Substudy 1.

10.5 Efficacy Subgroup Analysis

The subgroups listed below will be used in subgroup analyses of the primary endpoint.

- Sex (male, female)
- Age (\leq median, $>$ median)
- Race (white, non-white)
- Baseline corticosteroid use (yes, no)
- Baseline immunosuppressant use (yes, no)
- Baseline Adapted Mayo Score (≤ 7 , > 7)
- Baseline Adapted Mayo Score (\leq median, $>$ median)
- Baseline Full Mayo Score (≤ 9 , > 9)
- Baseline Full Mayo Score (\leq median, $>$ median)
- Prior exposure to anti-TNF (yes, no)
- Prior exposure to biologic therapy (yes, no)
- Baseline weight (\leq median, $>$ median)
- Presence of pancolitis at Baseline (yes, no)
- Disease duration at Baseline (\leq median, $>$ median)
- Baseline hs-CRP (≤ 5 mg/L and > 5 mg/L)

- Baseline hs-CRP (\leq median, $>$ median)
- Baseline Albumin (\leq median, $>$ median)
- Region (US versus non-US)

11.0 Safety Analysis

11.1 General Considerations

All safety comparisons will be performed between treatment groups and placebo group using the ITT1A and safety analysis sets. The safety variable will be summarized by treatment according to the treatment a subject actually received. The differences between treatment groups and placebo in safety parameters will be evaluated using two-sided tests at the significance level of 0.05.

Unless otherwise specified, the treatment group differences in continuous safety variables (e.g., change from baseline to final observation on laboratory tests) will be assessed using an ANOVA model with the term of treatment, and the treatment group differences in categorical safety variables will be evaluated using a Fisher's exact test.

Missing safety data will not be imputed.

11.2 Analysis of Adverse Events

Adverse events will be coded using the Medical Dictionary for Regulatory Activities (MedDRA). The actual version of the MedDRA coding dictionary will be noted in the clinical study report.

11.2.1 Treatment-Emergent Adverse Events

Treatment-emergent AEs during Substudy 1 are defined as events that begin or worsen either on or after the first dose of the study medication in Substudy 1 and within 30 days after the last dose of the study medication in Substudy 1 for subjects who discontinued Substudy 1 and are not enrolled into Substudy 3 or Study M14-533, or events that begin or worsen either on or after the first dose of the study medication in Substudy 1 and up to

the first dose of the study medication in Substudy 3 or Study M14-533. An overview of treatment-emergent AEs, including AEs of special interest such as adverse events leading to death and adverse events leading to early termination, AEs by MedDRA preferred term and system organ class, AEs by maximum relationship to study drug, and AEs by maximum severity will be summarized by number and percentage. Treatment group differences (each ABT-494 dose group versus placebo group, as well as ABT-494 dose groups combined versus placebo group) in the overall incidence of treatment emergent AEs will be assessed with Fisher's exact test for each preferred term for Substudy 1.

The number and percent of subjects experiencing treatment-emergent adverse events will be summarized for the following adverse event categories. Comparisons of the percent of subjects experiencing an adverse event between treatment groups and placebo will be performed using Fisher's exact tests. Only *P* values < 0.100 when rounded to three digits will be presented.

- Any treatment-emergent adverse event.
- Any treatment-emergent adverse event that was rated as possibly related to study drug by the investigator (Reasonable Possibility).
- Any treatment-emergent severe adverse event.
- Any treatment-emergent serious adverse event.
- Any treatment-emergent adverse event leading to discontinuation of study drug.
- Any treatment-emergent adverse event leading to death.
- Any treatment-emergent adverse event of special interest.

Treatment-emergent adverse events will be summarized as follows:

- Grouped by System Organ Class and Preferred Term.
- A by-subject listing will be provided.
- Grouped by System Organ Class, Preferred Term and Severity.
- Grouped by System Organ Class, Preferred Term and Relationship to Study Drug.

- Grouped by System Organ Class and Preferred Term with subject numbers.

In treatment-emergent AE tables, a subject who reports more than one treatment-emergent AE in different system organ classes will be counted only once in the overall total. A subject who reports two or more different preferred terms which are in the same SOC will be counted only once in the SOC total. A subject who reports more than one treatment AE with the same preferred term will be counted only once for that preferred term using the most extreme incident (i.e., most "severe" for the severity tables and most "related" for the relationship tables).

Adverse events will also be summarized by maximum severity. If a subject has an adverse event with unknown severity, then the subject will be counted in the severity category of "unknown," even if the subject has another occurrence of the same adverse event with a severity present. The only exception is if the subject has another occurrence of the same adverse event with the most extreme severity – "Severe." In this case, the subject will be counted under the "Severe" category.

Adverse events will also be summarized by maximum relationship to study, as assessed by the investigator. If a subject has an adverse event with unknown relationship, then the subject will be counted in the relationship category of "unknown," even if the subject has another occurrence of the same adverse event with a relationship present. The only exception is if the subject has another occurrence of the same adverse event with a relationship assessment of "Reasonable Possibility." In this case, the subject will be counted under the "Reasonable Possibility" category, respectively.

Incidence rates per 100 patient years of exposure to study drug will be presented for AE overviews and for AEs by SOC and preferred term where the number of events will be used as the numerator.

